1.3.2 Protego Animal Study

The safety and efficacy of the BIOTRONIK Linox^{smart} DF4 SD lead along with the Iforia or Ilesto 7 DF4 ICD (equivalent devices) were evaluated by comparison to the FDA-approved BIOTRONIK Linox^{smart} SD lead. The Protego family of ICD leads was developed and tested with the engineering project name “Linox^{smart} DF4”. Therefore, all references to this device name are synonymous with the Protego family of ICD leads.

The animal study began May 30, 2013, was randomized, and compared the two ICD systems implanted in a total of 24 healthy canine subjects (N=12/group) over a period of 12 weeks. Ventricular pacing capture threshold (PCT), painless shock impedance (PSI), serious adverse device event -free rate (SADE-free), R-wave amplitude, and ventricular pacing impedance (VPI) of the ICD systems implanted for 12 weeks were the focus of primary and secondary endpoints.

All primary endpoints were achieved, as the DF4 system demonstrated non-inferiority of PCT and equivalence of PSI in all three shock pathways relative to the DF-1 system, along with a 100% SADE-free rate. In addition, all secondary endpoints were achieved,

as the DF4 system demonstrated non-inferiority of R-wave amplitude and equivalence of VPI relative to the DF-1 system. The results of this study demonstrate that the BIOTRONIK Iforia/Ilesto DF4 ICD equipped with the Linx^{smart} DF4 SD lead is comparable in terms of efficacy and safety to its predecessor, the BIOTRONIK Iforia/Ilesto DF-1/IS-1 ICD equipped with the Linx^{smart} SD lead.

1.4 DEVICE DESCRIPTION

1.4.1 Protego Lead Description

The Protego ICD lead is a 7.8 F transvenous, steroid-eluting, endocardial lead for use with any ICD/CRT-D with a DF4 connector port (Figure 2). Protego leads are variants of currently marketed Linx^{smart} ICD leads with IS-1 and DF-1 connectors. The functionality of each lead is identical to the respective predecessor Linx^{smart} ICD lead.

The Protego S and Protego T leads have two sensing and pacing electrodes (distal tip and ventricular ring electrode) and one defibrillation electrode (ventricular shock coil). The Protego SD and Protego TD leads have two sensing and pacing electrodes (distal tip and ventricular ring electrode) and two defibrillation electrodes (ventricular and superior vena cava shock coils).

These leads, in conjunction with an ICD or CRT-D device, perform the following functions:

- sense electrical signals from cardiac tissue and conduct those signals to the device;
- conduct bradycardia and anti-tachycardia pacing pulses emitted from the device to cardiac tissue;
- conduct defibrillation shocks of both high and low energies from the device to cardiac tissue.

The Protego leads are intended for permanent placement in the right ventricle. The tip and ring electrodes form the most distal portion of the lead and provide dedicated bipolar sensing and pacing.

All Protego leads have one shock electrode that is positioned in the right ventricle. The Protego SD and Protego TD dual-coil ICD leads have an additional shock electrode for placement in the superior vena cava (SVC). All Protego leads feature Silglide® surface treatment, designed to reduce the force required to maneuver the lead during the implant procedure.

The Protego S and Protego SD leads feature an electrically active extendable/retractable fixation helix for use in lead placement. The helix is extended and retracted by rotating the contact pin with a fixation tool. Both the fixation helix and ring electrode are comprised of a platinum/iridium alloy base with fractal iridium. The Protego T and Protego TD leads feature a passive fixation tip coated with fractal iridium.

The distal tip of all Protego ICD leads consists of a steroid eluting collar which contains the active ingredient dexamethasone acetate (DXA). Upon exposure to body fluids, the steroid elutes from the collar. Release of the steroid is intended to decrease the inflammatory response at the contact site between the lead tip and the endocardium, thereby decreasing the elevated pacing thresholds of the endocardial lead that often occur after lead implantation.

The DF4 connector of Protego ICD leads was designed in compliance with ISO 27186; the specifications such as geometry, tensile loads, etc., of the DF4 connector meet the requirements of this standard. The DF4 connector allows use with ICDs/CRT-Ds that have connector ports conforming to ISO 27186.

[figure not shown]
Figure 2: Protego Lead

1.4.2 Design Differences between Protego and Linx^{smart}

Differences between the currently approved Linx^{smart} leads and the Protego leads are limited to the replacement of DF-1 and IS-1 connectors with a DF4 connector and a modified transition area between connector and lead body (Figure 3). The electrical components of Protego leads located from lead body to the lead tip remain unchanged compared to Linx^{smart} leads.

Figure 3: DF4 Connector and Lead

1.4.3 DF4 Device Header Description

The DF4 connector features a single connection between the ICD/CRT-D and the ICD lead. As a result, the number of connectors for ICD leads is reduced from two or three connectors for a single shock coil or a dual shock coil DF-1/IS-1 ICD lead (see Figure 4 and Figure 6), respectively, to a single connection with a DF4 ICD lead (see Figure 5 and Figure 7).

Figure 4: Linx^{smart} SD Schematic

[figure not shown]

Figure 5: Protego SD Schematic

[figure not shown]

Figure 6: Orientation of DF-1/IS-1 llesto Headers

[figure not shown]
[figure not shown]

Figure 7: Orientation of DF4/IS-1 llesto Headers

VR – Single Chamber Device, DR – Dual Chamber Device, HF – Triple Chamber Device

Due to these modifications, DF4 systems require a more complex design of the generator connector cavity. Three of the four setscrews that are necessary for a dual coil DF-1/IS-1 shock lead have been replaced by spring contacts. Additionally, strict requirements are put on the seals that have to prevent leaking current as well as prevent liquid from entering the header cavity. Conformity with this standard ensures that the DF4 generator connector can be connected to any DF4-labelled lead. For purposes of the Protego DF4 post-approval registry, the BIOTRONIK Protego ICD lead is required.

1.4.4 BIOTRONIK Home Monitoring®

Current expert consensus advocates 3- to 6-month device evaluations either in-person or by remote monitoring for ICD/CRT-D devices¹.

BIOTRONIK Home Monitoring® is a communication system which allows the automatic transmission of diagnostic patient data from the device to the physician at any time. The technology implements the use of wireless communications to provide the physician with daily patient monitoring and trend analysis information between office follow-up visits. A block diagram of the transmission path is shown in Figure 8, and the transmission steps are described as follows:

- Communication starts with the implant, which activates a very low power RF transmitter circuitry integrated within the pulse generator.
- The patient's device accepts patient data from the implant and transfers this digital information using a cellular short messaging system (SMS) or telephone landline connection to a BIOTRONIK Service Center for evaluation.
- The BIOTRONIK Service Center receives incoming data and generates a customized summary which is available to the physician online via secure Internet access, or can be forwarded to the physician via fax.

Figure 8: Home Monitoring® Transmission Path

[figure not shown]
¹ Wilkoff BL, et al. HRS/EHRA expert consensus on the monitoring of cardiovascular implantable electronic devices (CIEDs): description of techniques, indications, personnel, frequency and ethical considerations. *Heart Rhythm* 2008;5:907-25

BIOTRONIK conducted the TRUST study to evaluate the safety and effectiveness of Home Monitoring®. BIOTRONIK received FDA approval (P050023/S020, approved May 12, 2009) of the following labeling claims regarding Home Monitoring®:

- BIOTRONIK Home Monitoring® information may be used as a replacement for device interrogation during in-office follow-up visits.
- A strategy of care using BIOTRONIK Home Monitoring® with office visits when needed has been shown to extend the time between routine, scheduled in-office follow-ups of BIOTRONIK implantable devices in many patients. Home Monitoring® data is helpful in determining the need for additional in-office follow-up.
- BIOTRONIK Home Monitoring® patients—who are followed remotely with office visits when needed—have been shown to have similar numbers of strokes, invasive procedures and deaths as patients followed with conventional in-office follow-ups.
- BIOTRONIK Home Monitoring® provides early detection of arrhythmias.
- BIOTRONIK Home Monitoring® provides early detection of silent, asymptomatic arrhythmias.
- Automatic early detection of arrhythmias and device system anomalies by BIOTRONIK Home Monitoring® allows for earlier intervention than conventional in-office follow-ups.
- BIOTRONIK Home Monitoring® allows for improved access to patient device data compared to conventional in-office follow-ups since device interrogation is automatically scheduled at regular intervals.

In the Ilesio ICD and CRT-D devices, Home Monitoring® provides event and system information similar to what is currently available during office follow-up visits. The highlighted information in the Home Monitoring® Quick View Summary Report, Figure 9, displays the study related follow-up data automatically transmitted on a daily basis including: battery status, pacing impedance, pacing threshold, sensing amplitude (mean/min) for both the atrial and ventricular leads. In addition, Home Monitoring® provides automatic daily information on arrhythmias, lead trends, current device programming, event episodes, therapy provided, and long term data trends.

Figure 9: Home Monitoring® Quick View Summary Report

2. REGISTRY DESIGN

[figure not shown]
This multi-center, prospective, non-randomized registry is designed to gather safety data on BIOTRONIK's Protego leads. All subjects enrolled in the registry will be implanted with a US market released BIOTRONIK DF4 ICD or CRT-D pulse generator and a Protego lead.

Potential subjects will be identified by the investigator from their general patient population and must have an approved indication for receiving an ICD or CRT-D device. Additionally, potential subjects must satisfy the registry inclusion and exclusion criteria (Sections 3.1.3 and 3.1.4). If a patient has been determined to be eligible, informed consent is obtained prior to initiating any registry related procedures. After written informed consent has been obtained, enrollment visit data will be collected. Written informed consent and enrollment visit data collection may be obtained \pm 30 days from the date of implant. If consent is obtained and eligibility is determined prior to implant, patients are considered 'provisionally enrolled' until they are successfully implanted, at which time they are considered fully enrolled. Device data and any adverse events will be collected from the date the first implant attempt onwards. If a patient is enrolled post-implant, device data and any adverse events since the date of the first implant attempt will be collected retrospectively at the enrollment visit.

After enrollment, subjects will be seen for an evaluation at three and six months post implant, and every six months thereafter for five years. Subjects with Home Monitoring® capabilities will be seen for an in-office follow-up at least once every 12 months and have the option to substitute a Home Monitoring® follow-up for every other in-office follow-up to result in the six month follow-up schedule. Registry visits completed using Home Monitoring® data will be accompanied by a phone call to the subject for a short verbal assessment. Subjects without a Home Monitoring® system will be seen for an in-office follow-up at three and six months post implant, and at least once every six months thereafter.

Figure 10 provides an overview of the clinical registry design. Details of subject eligibility requirements are noted in Section 3.1 and details of other registry specific procedures and data collection are noted in Section 3.2 and Section 5.

Figure 10. Study Design Flowchart

2.1 REGISTRY ENDPOINTS

This registry includes the assessments of two primary safety endpoints related to the Protego DF4 lead, and several secondary endpoints that evaluate the safety and effectiveness of the BIOTRONIK ICD/CRT-D system with a Protego DF4 lead.

2.1.1 Primary Endpoint 1: Protego DF4 Lead Safety – 5-Year Adverse Event-Free Rate

The purpose of primary endpoint 1 is to evaluate the overall incidence of adverse events related to the Protego DF4 lead or header (as defined in Section 10) from implant through 5 years. Assuming that the expected Protego DF4 lead or header-related adverse event rate at 5 year post-implant (proportion of subjects with at least one AE in the timeframe from implant through 5 year post-implant) is 7.5% or less, then the primary safety endpoint will be evaluated in the following testable hypothesis in superiority format.

H₀: The adverse event-free rate (AEFR) for subjects receiving the Protego DF4 lead at 5 years post-implant is less than or equal to 92.5%

$$\text{AEFR} \leq 92.5\%$$

H_a: The adverse event-free rate (AEFR) for subjects receiving the Protego DF4 lead at 5 year post-implant is greater than 92.5%

$$\text{AEFR} > 92.5\%$$

A rejection of the null hypothesis would demonstrate that the adverse event-free rate is greater than 92.5%.

2.1.2 Primary Endpoint 2: Protego DF4 Lead Safety – Individual 5-Year Adverse Event-Free Rates

Each of the individual types of adverse events contributing to primary endpoint 1 will be evaluated separately in the following superiority hypothesis.

H₀: The individual adverse event rate (AEIndividual) for a given type of AE for the Protego DF4 lead at 5 years post-implant is greater than or equal to 1%

$$\text{AEIndividual} \geq 1\%$$

H_a: The individual adverse event rate (AEIndividual) for a given type of AE for the Protego DF4 lead at 5 years post-implant is less than 1%

$$\text{AEIndividual} < 1\%$$

If the two-sided, 95% upper confidence bound is no more than 1% for individual adverse events, then the null hypothesis will be rejected for that AE type.

2.1.3 Secondary Endpoints

There are no formal tests of hypotheses associated with secondary endpoints 1-3.

1. Pacing threshold, sensing and impedance measurements for the Protego DF4 lead through 5 years post-implant.
2. Shock impedance for the Protego lead through 5 years post-implant.
3. Adverse event rates for protocol defined, CEC adjudicated AEs excluded from primary safety endpoints 1 and 2, through 5 years post-implant.

2.1.4 Additional Data of Interest

Additional information will be collected to characterize the registry population, implanted system, and progress of the registry. The collected information will include baseline demographics, medical history, implanted system, system revisions, Protego extractions, returned product analysis, and compliance. Specifically, data of interest will include:

- Baseline demographics, including age, gender, weight, height, New York Heart Association (NYHA) class, ejection fraction, and race and ethnicity (optional)
- Medical history, including indication for device
- Implanted device data, including pulse generator and leads models, serial numbers, and implant dates from initial implant and/or revisions
- Implant procedure data (collected retrospectively if implant occurred prior to enrollment)
- Pacing threshold, sensing and impedance measurements for implanted BIOTRONIK RA and LV leads
- Site reported adverse events excluded from primary and secondary endpoint analysis
- Protego DF4 extraction experience
- Results from returned product analysis
- Compliance to protocol requirements and registry visit schedule

2.2 REGISTRY SIZE

To document the clinical experience of the Protego DF4 lead as required by the FDA, the Protego DF4 post-approval registry is designed to follow 1694 subjects for 5 years post-implant at up to 75 U.S. and International sites.

The investigation is designed to limit the number of patients involved while still exposing the device to a sufficiently large patient population in order to ensure a representative and statistically meaningful sample.

2.3 SAMPLE SIZE ANALYSIS

The estimated sample sizes required to evaluate primary endpoints 1 and 2 are based on a superiority comparison of the overall Protego DF4 lead AE free-rate to 92.5% at 5 years, and a non-powered, superiority comparison for those individual lead-related AEs to 1% at 5 years. The sample size for primary safety endpoint 1 was calculated based on the following assumptions:

Assumptions for primary safety endpoint 1

- Study Design: nonrandomized registry
- Test basis: exact binomial test
- Type I error (alpha): 0.025 (one-sided for superiority)
- Statistical power: 80%
- Estimated AE-Free Rate at 5 years: 95.0% for Protego Leads
- Performance goal for AE-Free Rate at 5 years: 92.5%

For primary safety endpoint 1, a total of 750 evaluable Protego leads would be required to demonstrate superiority to an AE free-rate of 92.5% (see Table 3). Assuming a 10% loss to follow-up rate per year over 5 years of follow-up (average of 8.2% of original population per year), a total of 1271 ($=750/0.9^5$) subjects with an ICD lead would be required to be enrolled to evaluate primary safety endpoint 1.

Assumptions for primary safety endpoint 2

- Estimated individual AE rate at 5 years: 0.4%
- Allowable two-sided, upper 95% confidence bound: 1%

For primary safety endpoint 2, a total of 1000 evaluable subjects with Protego DF4 leads would be required to demonstrate a two-sided, upper 95% confidence bound of 1%, assuming an expected individual AE rate of 0.4% (see Table 3). Assuming a 10% loss to follow-up rate per year over 5 years of follow-up (average of 8.2% of original population per year), a total of 1694 ($=1000/0.9^5$) subjects would be required for evaluation of primary safety endpoint 2.

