2.3.1 Attrition

For the sample size calculation, a maximum loss to follow-up of 10% per year (41% over 5 years) was assumed. The loss to follow-up rate encompasses all causes for subjects to be exited from the registry, including death, device explants, subject directed withdrawals, physician-directed withdrawals, and loss of contact with the subject.

Table 3: Primary Safety Endpoints Sample Sizes

	Primary Safety Endpoint 1	Primary Safety Endpoint 2
Sample Size of Evaluable Subjects	750 subjects	1000 subjects
Total Adjusted for Attrition	1271 subjects	1694 subjects

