2.4.1 Endpoint Analysis

Primary safety endpoint 1 will be evaluated by performing an exact binomial test comparing the observed proportion (overall AE free-rate at 5 years) to 92.5%. Equivalently, the two-sided 95% lower confidence bound for the absolute difference between the overall AE free-rate and 92.5% must exceed zero.

The evaluation of primary safety endpoint 2 will be based on the exact, two-sided 95% confidence interval for the observed, individual AE rates at 5 years. The upper bound of these 95% confidence intervals must be less than 1%.

Secondary endpoints 1 and 2, which summarize pacing thresholds, sensing, impedance measurements and shock impedance measurements for the Protego lead, will be reported via standard measures, including means, standard deviations, medians, minimums, and maximums.

Secondary endpoint 3, which includes AEs that were excluded from primary safety endpoint 1, through 5 years post-implant will also be summarized as AE rates together with their associated, exact 95% confidence intervals.

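### At 1000 evaluable subjects, the 4 events expected for endpoint 2 give an exact upper bound of 1.021%, so the plan's own planning case misses its 1% limit; only 3 or fewer events pass

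*Combined protocol and SAP*

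**What the plan says.** Section 2.3 gives two planning inputs for primary endpoint 2: "Estimated individual AE rate at 5 years: 0.4" per cent and "Allowable two-sided, upper 95% confidence bound: 1" per cent. From these it concludes that "a total of 1000 evaluable subjects with Protego DF4 leads would be required to demonstrate a two-sided, upper 95% confidence bound of 1" per cent. Table 3 repeats the 1000 and inflates it for attrition to 1694, which is the enrolment target of the registry. Section 2.3.1 describes that attrition: "a maximum loss to follow-up of 10% per year (41% over 5 years) was assumed".

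The method is fixed in Section 2.4.1, where the evaluation is "based on the exact, two-sided 95% confidence interval for the observed, individual AE rates at 5 years". The pass rule appears in two forms:

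- Section 2.4.1: "The upper bound of these 95% confidence intervals must be less than 1" per cent.
- Section 2.1.2: "If the two-sided, 95% upper confidence bound is no more than 1% for individual adverse events", the null hypothesis is rejected for that AE type.

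Section 2.3 also describes endpoint 2 as "a non-powered, superiority comparison for those individual lead-related AEs to 1% at 5 years".

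**The concern.** The sample-size statement and the analysis rule should agree when the planning assumption comes true exactly. A rate of 0.4% in 1000 subjects is 4 events, so 4/1000 ought to meet the criterion. If it does not, the number that sizes the registry fails to deliver the precision claimed for it.

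A reader of Section 2.3 would also take 4 events of one type as a pass when the plan's own interval says otherwise. Endpoint 2 is a primary endpoint with a reject-or-not decision for each AE type, so the status of a 4-event result should be settled before the data are seen.

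**Working it through.** **Inputs.** Evaluable n = 1000, expected rate 0.4%, limit 1% and attrition of 10% per year for 5 years (Section 2.3); exact two-sided 95% interval (Section 2.4.1).

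**The plan's enrolment figure.** 1000 / 0.9^5 = 1000 / 0.59049 = 1693.5, rounded up to 1694. This reproduces.

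**Expected events.** 0.004 × 1000 = 4.

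**Exact upper bound.** For x events in n subjects, the two-sided 95% Clopper-Pearson upper bound is the 0.975 quantile of a Beta(x + 1, n − x) distribution. At n = 1000:

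| Events | Upper bound | Meets 1% limit |
|---|---|---|
| 2 | 0.721% | yes |
| 3 | 0.874% | yes |
| 4 | 1.021% | no |
| 5 | 1.163% | no |

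The same result as a test with 0.025 in the tail, for X ~ Binomial(1000, 0.01):

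- P(X ≤ 4) = 0.0287, above 0.025, so 4 events do not reject.
- P(X ≤ 3) = 0.0101, so 3 events do.

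**Where 4 events start to pass.** The bound for 4/1021 is 1.00003% and for 4/1022 is 0.9991%. The smallest n is therefore 1022, which is 22 (2.2%) above 1000. The largest passing count by number evaluable is:

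| Evaluable | Largest passing count |
|---|---|
| 874 to 1021 | 3 |
| 1022 to 1163 | 4 |
| 1164 to 1302 | 5 |

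**In terms of enrolment.**

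- By the plan's inflation rule, 1022 / 0.9^5 = 1730.8, or 1731 enrolled.
- With 1694 enrolled, 1022 evaluable needs total attrition of 1 − 1022/1694 = 39.7% instead of 41%. Per year that is 1 − (1022/1694)^(1/5) = 9.6%.

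**Does another interval rescue the statement?** At 4/1000 other intervals also exceed 1%: Blaker about 1.005%, Sterne about 1.03%, Wilson 1.024%, exact Poisson 1.024%. Four events pass only under methods the plan does not specify: one-sided 95% exact (0.913%), mid-P (0.962%), Jeffreys (0.948%) and Wald (0.791%).

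**Chance of meeting the criterion, as context for a non-powered comparison.** These are binomial probabilities for one AE type:

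| True rate | 1000 evaluable, P(X ≤ 3) | 1022 evaluable, P(X ≤ 4) |
|---|---|---|
| 0.4% | 43% | 61% |
| 0.25% | 76% | 88% |
| about 0.23% | 80% | not computed |

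**The case against.** The best case for leaving the text alone has four parts.

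1. **Rounding.** Section 2.3 presents its sizes as estimates from inputs given to one decimal at most, and 1.021% is 1% at that precision. But Sections 2.1.2 and 2.4.1 state a pass/fail limit with no rounding allowance, and 1.021% is above it.

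2. **Non-powered.** The plan promises no probability of success for endpoint 2. That is correct, and the 43% breaks no commitment. It does not cover the separate statement about what 1000 subjects demonstrate, which is a claim about precision.

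3. **The evaluable number may exceed 1000.** Section 2.4.3 keeps subjects who had an AE before 5 years even if they later exit, whereas the inflation to 1694 removes every exit. Take the plan's overall 5% AE rate, exits independent of AEs, and any primary AE keeping a subject evaluable. With constant hazards λ = −ln(0.9) = 0.1054 for exit and μ = −ln(0.95)/5 = 0.0103 for AE, the evaluable fraction is 0.9^5 × 0.95 + [μ/(μ + λ)] × (1 − 0.9^5 × 0.95) = 0.561 + 0.039 = 0.600, or about 1016 of 1694. If every AE fell at the start, it is 0.05 + 0.95 × 0.59049 = 0.611, or about 1035. So 1022 could be reached without extra enrolment, and 1731 should not be read as a requirement. However, the plan does not say whether an AE of one type keeps a subject evaluable for another type, and the constant-hazard figure still falls short of 1022. Nor does Section 2.3 rely on this argument; its claim is made at 1000.

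4. **No decision changes.** The final analysis applies the exact bound at the observed n, whatever Section 2.3 says. This stands and limits the severity. It also stands that the two forms of the rule give the same result at every count and denominator examined here, so harmonising them is tidiness.

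**Conclusion.** The concern holds. Under the interval the plan specifies, the result it plans for (4 events in 1000) has an upper bound of 1.021% and fails both forms of the rule. The true limit at 1000 evaluable is 3 events, an observed rate of 0.3%.

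The error is real but small: 22 evaluable subjects. The test, its error control and the enrolment target need not change. It is worth correcting because the 1000 sizes the registry, the endpoint is primary, and an uncorrected statement invites dispute over a 4-event result, which prints as 1.0% to one decimal.

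The conclusion rests only on the plan's own n, rate, interval and limit. The pass probabilities also assume binomial sampling at the stated true rate.

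**What to change.** Keep 1000 evaluable and 1694 enrolled, and make three text changes.

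- **Section 2.3.** Replace the endpoint 2 statement with wording such as: *With 1000 evaluable subjects, the criterion is met for an AE type with 3 or fewer events (exact two-sided 95% upper bound 0.874%); 4 events give 1.021% and do not meet it. Four events meet it if at least 1022 subjects are evaluable. The comparison is not powered; for context, the probability of meeting the criterion with 1000 evaluable is about 43% at a true rate of 0.4%, 76% at 0.25% and 80% at about 0.23%.*
- **Table 3.** Add a row for endpoint 2 giving the maximum number of events of one type that meets the criterion: 3 at 1000 evaluable, 4 from 1022.
- **Sections 2.1.2 and 2.4.1.** Use one form of the rule and state that the bound is compared with 1% unrounded.

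The first change is the essential one. The cost is a few sentences and one table row, with no added subjects and no change of test. The stated planning figure becomes slightly less favourable.
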